### **Hypothesis:**

Since there are no previous studies comparing LCD vs. MD the premise is that the diets have equal effect with no superiority or inferiority.

Our Primary end point is to compare the impact of LCD and MD on the time in range (TIR) 70-180 mg/dl assessed by Continuous Glucose Monitoring (CGM) among adolescents with T1DM.

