#### *Glycemic variability*

Glycemic variability from continuous blood glucose monitoring (Libre, Medtronic, Dexcom) and included SD Time spent in range 70-180 mg/dl, Time between 70-54mg/dl, time under 54 mg/dl and CV (coefficient variant) assessed by CGM was downloaded at each visit (baseline, and weeks 1,2,4,7,10 and 12) with the dietician.

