## **Statistical Analysis**

The sample size was based on the primary endpoint, ie delta in the time spent in range (TIR 70-180 mg/dl). To be able to detect a difference of 20% with 80% power at a 5% significance level with a two-sided paired t-test. Thirty-four participants should complete the study. To account a 40% attrition rate, we included a total of 40 participants in the study. The sample size was calculated using PASS 2020 software.

Data will be analyzed with the IBM SPSS software (IBM SPSS Statistics for Windows, Version 24;IBM Crop., Armonk, NY, USA, 2016). Categorical variables were assessed for frequency and percent. Continuous variables described as frequency and percent. Continuous variables were assessed for normal distribution using histogram and Q-Q plots. Normally distributed continuous variables were described as means and standard deviations (SD), and non-normally distributed parameters were described as median and interquartile rang (IQR). Categorical variables in the same group were compared using a dependent sample t test. Differences between groups in continuous data were compared using independent-sample t tests (normally distributed data) or Mann-Whitney test (skewed data). For variables that were non-normally distributed, the median interquartile range (IQR) were presented and Kruskal-Wallis test was applied to evaluate he differences.

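### The primary TIR comparison is tied to unadjusted one-value-per-person tests, although TIR is downloaded serially and 40% attrition is expected

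*Protocol*

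**What the plan says.** The Hypothesis section sets the primary aim as a between-diet contrast: to "compare the impact of LCD and MD on the time in range (TIR) 70-180 mg/dl assessed by Continuous Glucose Monitoring (CGM"). The Statistical Analysis section calls the primary variable "ie delta in the time spent in range (TIR 70-180 mg/dl") and does not say which two time points, or which summary of visits, make up the delta.

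For between-group comparison of continuous data the same section gives one general rule: "Differences between groups in continuous data were compared using independent-sample t tests (normally distributed data) or Mann-Whitney test (skewed data"). Kruskal-Wallis is mentioned for non-normal variables. Each of these takes one number per participant, and none adjusts for baseline.

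The Glycemic variability section has CGM measures, TIR among them, "downloaded at each visit (baseline, and weeks 1,2,4,7,10 and 12) with the dietician". The Glycemic control section has TIR downloaded at every dietitian visit, and the Diet intervention section lists a dietitian visit at week 24. There are therefore six post-baseline downloads on the first reading and seven if the other two sections are read together.

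On loss to follow-up the plan states: "To account a 40% attrition rate, we included a total of 40 participants in the study".

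**The concern.** The trial collects a series of TIR values on each participant, but the named tests use a single number. Someone who leaves at week 8 already has four on-diet values (weeks 1, 2, 4 and 7). If the delta needs a final-visit value and none is imputed, that person drops out of the primary analysis.

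Two things are at stake. The first is precision, in a trial of 40. The second is bias. The trial is open label and participants use their own CGM devices, so a participant on one diet can see poor TIR and leave. The completers on that diet then look better than the diet is. The interim downloads carry the information that would largely correct this.

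**Working it through.** **Inputs.** From the Statistical Analysis section: a difference of 20% (taken here as percentage points, which the protocol does not say), 80% power, two-sided 5%, 34 completers, 40 enrolled, 40% attrition. From Participants and study design: 1:1 allocation. Assumed, because the protocol gives no figure: the SD of the delta, the correlations between visits and the drop-out mechanism.

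**The plan's own figure.** The sizing is "with 80% power at a 5% significance level with a two-sided paired t-test". Without an SD, 34 cannot be reproduced. Back-solving gives SD 40.4 for a paired test on 34 pairs, or SD 20.2 for an independent test with 17 per arm. The second matches the parallel design and is used for the power figures below. Separately, 34/(1 - 0.40) = 57, not 40; 40 fits 15% loss (34/0.85 = 40). Precision is therefore shown at both 15% and 40%.

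**Cost of losing leavers.** At 40% loss, 40 x 0.6 = 24 remain, 12 per arm. With SD 20.2, power of the t-test on the delta falls from 80% (17 per arm) to about 64%.

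**Baseline adjustment alone.** With equal variances and baseline-to-final correlation r, the delta has variance proportional to 2(1 - r) and ANCOVA to 1 - r². The ratio is (1 + r)/2: 0.65, 0.75, 0.85 and 0.90 for r = 0.3, 0.5, 0.7 and 0.8. Power at 12 per arm becomes about 82%, 76%, 71% and 69%.

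**All visits, random drop-out.** Variance of a longitudinal week-12 estimate divided by that of the completers' delta (20 per arm, 1,500 runs, covariance treated as known):

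| Pattern | No loss | 15% loss | 40% loss | SE at 40% loss |
|---|---|---|---|---|
| Compound symmetry, 0.5 | 0.75 | 0.72 | 0.71 | 8.45 to 7.13 |
| Participant effect plus serial correlation | 0.79 | 0.78 | 0.71 | 8.36 to 7.03 |
| Compound symmetry, 0.7 | 0.85 | 0.82 | 0.75 | 8.61 to 7.48 |

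The reduction at 40% loss is 25-29%. A second set (2,000 runs, three other correlation patterns, 38-41% loss, known covariance) gave 27-38%, of which about 10-15% was beyond completers' ANCOVA.

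With an estimated covariance (participant effect plus serial correlation, only 120 runs per setting), the SD of the estimate was:
- Compound-symmetric data: 6.6, against 7.6 (delta) and 7.3 (ANCOVA). (6.6/7.6)² = 0.75 and (6.6/7.3)² = 0.82.
- Autoregressive data: 6.1, against 7.7 and 6.5. (6.1/7.7)² = 0.63 and (6.1/6.5)² = 0.88.

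Rejection under the null was 3-6%.

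**Bias when LCD drop-out follows a poor last TIR change, true difference 0 (points).** The rows come from separate simulations with different drop-out strengths, so compare within rows.

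| Truth and fitted covariance | Delta t-test | Completers' ANCOVA | Longitudinal |
|---|---|---|---|
| Three patterns, known covariance | +3.9 to +4.8 | +2.4 to +2.6 | -0.3 to +0.1 |
| Autoregressive, true covariance | +5.7 | +3.7 | -0.1 |
| Autoregressive, working compound symmetry | +5.7 | +3.7 | +2.8 |
| Compound symmetry, estimated random intercept | +5.0 | +2.6 | +0.5 |
| Partly autoregressive, estimated random intercept | +3.7 | +2.8 | +1.8 |
| Compound symmetry, estimated participant effect plus serial correlation | +7.1 | +3.6 | -0.8 |

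The last row has 120 runs. Its Monte Carlo error is about 6.6/√120 = 0.6 (SD taken from the random drop-out run), so -0.8 is compatible with no bias. That model was not checked under autoregressive data with informative drop-out.

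A covariance that ignores serial correlation leaves about half the bias where serial correlation exists (2.8/5.7 and 1.8/3.7, both 0.49). The misspecified random intercept with a Wald test also rejected a true null in 16% of 300 runs.

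**The case against.** A reader might infer that the plan discards all interim data and drops everyone without the last download. The protocol does not say so. It defines neither the time points of the delta nor an analysis set nor an imputation rule. A t-test can be run on any one-number summary, including the mean of on-diet downloads minus baseline, which would use the interim values. The exclusion of early leavers is therefore conditional: it follows if the delta ends at a final visit and nothing is imputed.

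A second objection is that missing-data handling and model detail usually sit in the SAP, which is not shown, and that the quoted sentence is a general rule for continuous data that does not name TIR. An unadjusted t-test in a randomised trial is also valid in itself. This has force against treating silence on imputation as an error. It does not answer the remaining point: the protocol does name methods, and none of them uses serial values or the baseline.

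A third objection is that the gain can be overstated, and this stands. Most of the precision comes from baseline adjustment. Averaging weeks 7, 10 and 12 cuts the variance of the change to (4/3)(1 - r)/[2(1 - r)] = 0.67 under compound symmetry. It is tempting to quote the resulting power, but that average is a different estimand and its power does not carry over to a test at one primary visit. If the delta ends at week 24, the week-12 figures are only indicative.

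**Conclusion.** The concern holds in conditional form. For an undefined delta in TIR, the protocol names only unadjusted one-value tests while scheduling six or seven post-baseline downloads and expecting 40% attrition. A better analysis of data already scheduled is available.

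Under the assumptions above, variance falls by roughly 25-38% against the t-test on the delta. The interim visits account for about 10-15% beyond ANCOVA, given a well-specified covariance. If LCD drop-out follows poor TIR, the t-test on the delta showed a spurious 3.7 to 7.1 points in favour of LCD, which is 19-36% of a 20-point target (3.7/20 and 7.1/20). A longitudinal model removes most of this when its covariance is adequate and about half when serial correlation is ignored. SD, correlations and drop-out mechanism are all assumed. This is a weakness in efficiency and robustness and does not make the named test invalid.

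**What to change.** In the Statistical Analysis section, name the primary visit and state that:

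- The LCD-MD difference in TIR is estimated in all randomised participants from all scheduled downloads, with a mixed model for repeated measures containing visit, diet, diet-by-visit and baseline TIR, read at the primary visit.
- The covariance structure is pre-specified and allows serial correlation as well as a participant effect, not compound symmetry alone. Small-sample degrees of freedom are used.
- The t-test (or Mann-Whitney test) on the delta is kept as a sensitivity analysis.

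The sections on glycemic control, glycemic variability and diet intervention should also agree on whether week 24 has a TIR download.

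The cost is a few sentences, with no extra visit or participant. SPSS, the named software, fits mixed models; confirm that the chosen structure is available in the stated version. The downside is that validity rests on data being missing at random given observed TIR, and on an adequate covariance model estimated from about 40 people. An average over weeks 7 to 12 may be added as support, labelled as a separate estimand.
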